**[Short title: U=U]**

Protocol Version: 1.0  
Version Date: October 31, 2019  
NCT04364165

Study Sponsors  
Bill and Melinda Gates Foundation

Question:	Can messaging about being undetectable equals untransmittable (U=U) increase HIV testing uptake in men?
Purpose:	HIV testing is the gateway to HIV prevention, treatment and HIV control, but uptake is suboptimal in South African men. Consequently, men have poor HIV outcomes including lower HIV testing uptake, lower ART initiation and a lower proportion achieving viral suppression. This study will investigate the effect of participatory, user-designed messaging to increase knowledge about U=U on HIV testing uptake in men in the Klipfontein Mitchells Plain (KMP) district in Cape Town, through a randomized trial design.
Primary objectives:	
1) To develop U=U messaging that encourages HIV testing uptake in men using a participatory, user-centered design. Messaging will seek to assuage the fears of testing HIV positive by conveying the message that HIV treatment makes it possible for HIV positive people to be untransmittable and to live normal lives.
 
2) To investigate the effect of U=U messaging on HIV testing uptake in men compared with the standard of care messaging.

Design:	
The study will be conducted in two phases:
 
Phase 1 is a participatory, human-centered design framework that will be used to develop U=U messages to increase HIV testing uptake in men.
 
Phase 2 is a cluster randomized trial that will determine the effect of U=U messaging on HIV testing uptake. Men in the intervention group will receive invitation cards for mobile HIV testing that contain U=U messages. Men in the control group will receive invitation cards for mobile HIV testing that contain standard messaging. Mobile clinic days (i.e. clusters of men receiving invitation cards at one site on one day) will be the unit of randomization.
 
The primary outcome will be HIV testing uptake at a community-based mobile clinic. Secondary outcomes will include the proportion of males tested who are HIV-positive and newly HIV positive.

Study setting and population:	KMP is a resource-limited, densely populated, high HIV disease burden area in Cape Town, where the use of health services among men is sub-optimal. Recruitment will be conducted by trained mobile clinic staff at high foot-traffic sites in the KMP community. Recruitment efforts will focus on young men in multiple mobile testing sites that are located in areas within KMP where there is a high burden of HIV.
Study size:	
In phase 1, approximately 20 men will be invited to participate in formative research through insight workshops for U=U message development. After the initial message development, about 20 more men will be invited to give feedback and suggest improvements to ensure understanding and acceptability of the messaging.
 
In phase 2, 40 clinic days will be randomized to intervention or control, with 100 men in the vicinity of the Tutu Tester receiving invitation cards for testing on each day (N=4,000).

Process:	In phase 1, mobile clinic staff will invite men to participate in an insight workshop at a community location. Men who agree to participate will respond to questions and take part in group brainstorming activities that will inform development of U=U messaging.

	
The research team will map the ideas and themes and use these to create an invitation to men. Their feedback will be used to calibrate the messages for the phase 2 trial.
 
In phase 2, a trained recruiter will deliver a U=U invitation message on intervention days and standard HIV testing messaging on control days to encourage HIV testing at a mobile clinic. On each day, recruiters will deliver about 100 invitation cards to young men in the vicinity of the mobile testing van where free HIV testing will be available.

Duration:	Phase 1 will run for one month. Phase 2 will run for 3 months.
Analysis:	In phase 1, acceptability will be measured through workshop feedback. In phase 2, a chi-squared test will estimate the effect of U=U messaging on HIV testing uptake compared with standard of care. We will also compare HIV positivity by study arm. Logistic regression analysis will model the effects of participant demographics, binary line of sight of mobile clinic, and time of day on testing uptake and time to presentation at the clinic.
Abstract:	HIV testing is the gateway to HIV prevention, treatment and HIV control, but uptake is suboptimal in South African men. Consequently, men have poor HIV outcomes including lower HIV testing uptake, lower ART initiation and a lower proportion achieving viral suppression. This study will investigate the effect of participatory, user-designed messaging to increase knowledge about U=U on HIV testing uptake in men in a high HIV disease burden area in Cape Town, through a clustered experimental design. This project has two main objectives. The first is to develop a U=U message that encourages HIV testing uptake in men using a participatory, user-centered workshops. Messages will seek to assuage the fears of testing HIV positive by conveying the message that HIV treatment makes it possible for HIV positive people to be untransmittable and to live normal lives. Second, the study will investigate the effect of U=U messaging on HIV testing uptake in men compared with the standard of care messaging. This study will utilize the DTHF Tutu Tester program, a mobile HIV clinic, to trial this new messaging intervention.

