**2.4.a. Design** – In phase 1, we will develop a U=U message using a participatory, human-centered design framework. There is increasing recognition that intervention design should incorporate viewpoints from the target audience to enhance collaboration, improve acceptability, and increase uptake (Byrne & Sahay, 2007; Mabunda, Khoza, Van den Borne, & Lebese, 2016). Thus, this participatory research will include workshops of approximately 40 men from a population that may potentially be recipients of the intervention.

**2.4.b Process** – Mobile clinic staff will invite approximately 20 men from high traffic locations in the KMP region to participate in design workshops for the development of a U=U message, that even if HIV positive they can be untransmittable, to normalize HIV and mitigate the fears of testing HIV positive. Each workshop participant will be asked to give informed consent, and then a trained facilitator will present the U=U message to the participants and facilitate the group to develop a message that resonates with them in language that is sufficiently colloquial to enable easy understanding among local

men. Their suggestions and statements will be recorded in written form verbatim and used to generate the invitation message. Once developed, the message will be presented to approximately 5-10 more men from within the community who will be invited to rate and suggest improvements to the acceptability of the prototype message. Following this exercise, the message will be fine-tuned and the final message will be printed on invitation cards for the phase 2 randomized trial.

## 2.5. Phase 2

2.5.a. Design – In phase 2, a cluster randomized trial will be conducted to determine the effect of the U=U message on HIV testing uptake. Individual mobile clinic days (i.e., the tester being parked at one site for one day) will serve as the unit of randomization, with each site day being assigned to the treatment or control condition via a computer-generated randomization process. Randomization will be stratified by testing location so that an equal number of clinic days at each location within KMP are assigned to each study group. On each mobile clinic day during the study, men in the vicinity of the mobile clinic will be offered invitation cards for same-day testing. Invitation cards will have unique identification codes. The information content on the referral cards and the mobilization approach will vary depending on condition.

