2.5.b. Intervention group – Following phase 1, the final U=U messages will be printed on invitation cards to be distributed at mobile testing sites. Messages will seek to assuage the fears of testing HIV positive by conveying the message that HIV treatment makes it possible for HIV positive people to be untransmittable and to live normal lives. Messages will encourage men to come in for HIV testing at the mobile clinic on the same day. A mobile clinic recruiter will deliver the invitation and share a brief script explaining U=U.

2.5.c. Control group – The standard invitation cards used at the Tutu Tester contain basic information encouraging HIV testing. Messages will encourage men to come in for HIV testing at the mobile clinic on the same day. A mobile clinic recruiter will deliver the invitation and share a brief script including the standard Tutu Tester message.

2.5.d. Study Instruments: Invitation cards – After mobile clinic recruiters deliver the invitation card and scripted verbal message, they will request the participant bring the card with them if they return to test. The card will contain the distribution date and time and recruiter information. The recruiter will also separately record the date and time the invitation was delivered, and whether the mobile clinic was visible on the card. When the participant returns to visit the mobile clinic, the recruiter will request the card and record the date and time of presentation as well as the unique identification code on the card. The participant will then be invited by a counsellor into a cubicle in the mobile clinic to complete a rapid HIV test after the counsellor consents the participant.

2.5.e. Study Instruments: Questionnaire – Key information will be collected from participants who come for testing via tablet. This intake will be completed immediately after an individual arrives at the Tutu Tester and presents their card. This will include a confirmation of inclusion criteria to ensure that the men are at least 18 years old. Other key information will include: type of message (intervention or control), line of sight, date and time of message delivery, date and time of presentation for HIV testing,

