time taken to get tested, age, whether the participant brought a peer or partner, whether the person stayed for an HIV test or not and HIV status. Several open-ended questions to learn about men's perceptions of the U=U messaging may also be asked including: if they had any previous understanding of U=U, what they think about the message and how this might change their behavior. The DTHF team will translate and validate the questionnaire and confirm its cultural appropriateness. As per standard operating procedure, those who test HIV positive will receive post-test counselling and assessment by a nurse and will be referred to their preferred clinic facility for HIV treatment.

2.5.f. Sample size and power calculations – In phase 2, the DTHF Tutu Tester will circulate between approximately four different locations within KMP. The Tutu Tester will be based in only one location on any given day. Clusters will comprise men who receive invitation cards on the same clinic day. Power calculations assumed 8 percent HIV testing uptake among men in the control group (based on two operational pilots conducted by our team) and an intraclass correlation of 0.02. With 40 clinic days in the study and 100 men within the vicinity of the Tutu Tester receiving invitation cards on each clinic day, we will have 80 percent power to detect a difference in HIV testing between groups of at least 5 percentage points.

2.5.g. Outcomes and analysis – The primary outcome will be HIV testing uptake, measured at the Tutu Tester based on presentation of the invitation cards. A chi-squared test will be conducted to estimate the effect of the intervention on HIV testing uptake. Logistic regression models will also be estimated to control for location, time of day, and distributor effects. Additional outcomes examined will include the proportion of males tested who are HIV-positive (and newly HIV positive).

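### Time to presentation is a duration seen only in men who return, yet it is assigned to logistic regression with no cut-off and no rule for non-presenters; van closing time can bias its time-of-day effect

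*Combined protocol and SAP*

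**What the plan says.** The Analysis row of the synopsis states: "Logistic regression analysis will model the effects of participant demographics, binary line of sight of mobile clinic, and time of day on testing uptake". The same sentence carries on to a second outcome, so the whole clause concerns "time of day on testing uptake and time to presentation at the clinic". It gives no threshold, time scale or censoring rule.

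Section 2.5.a sets the window: "men in the vicinity of the mobile clinic will be offered invitation cards for same-day testing". Sections 2.5.b and 2.5.c repeat it for both arms: "Messages will encourage men to come in for HIV testing at the mobile clinic on the same day". Section 2.5.f adds: "The Tutu Tester will be based in only one location on any given day".

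Section 2.5.d defines the two ends of the interval. The start is logged for every card: "The recruiter will also separately record the date and time the invitation was delivered". The recruiter's record also covers whether the van could be seen. The end is logged only for a man who comes back, when "the recruiter will request the card and record the date and time of presentation". Age and the other intake items in section 2.5.e have the same limit: "Key information will be collected from participants who come for testing via tablet".

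Section 2.5.g, the analysis section of the body, names testing uptake and HIV positivity among men tested. It does not mention time to presentation and offers no other model for it.

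**The concern.** There are three linked difficulties.

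- **Model and outcome do not match.** Logistic regression needs a binary outcome. Without a stated cut-off, the analyst must choose one after seeing the data or use another model.
- **Most cards have no value.** The delay exists only for men who return. The plan does not say whether the others are dropped, censored or counted as not having come in time.
- **A named predictor sets the ceiling of the outcome.** With same-day cards, the hour of delivery fixes how long a delay can be before the van closes. A late card can yield only a short delay.

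If only presenters are analysed, the report could say that men invited late in the day come faster when they merely had less time. That could mislead anyone using the result to schedule recruiters.

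**Working it through.** **1. The plan's own figure.** Section 2.5.f gives 40 days of 100 men, 8% control uptake, an intraclass correlation of 0.02, and 80% power for 5 points. The significance level is not stated; I assume two-sided 0.05.

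- Design effect: 1 + 99 × 0.02 = 2.98. Effective size per arm: 2,000 / 2.98 = 671.
- Power for 8% versus 13%: 84.9% by the plain z-test, and 80.9% with a continuity correction and a t reference on 38 df.
- Difference detectable at 80% power: 4.65 points (z) or 4.77 points (t, 38 df), which rounds to 5.

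The stated power is therefore reproducible. This point does not depend on it; it only supplies the planning rates.

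**2. Cards that would have a time.** I treat men tested as men who presented; any who present but leave untested would raise the count somewhat.

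- Control: 0.08 × 2,000 = 160. Intervention: 0.13 × 2,000 = 260.
- Total: 420 of 4,000 = 10.5%, leaving 3,580 (89.5%) without a time.
- With no effect: 0.08 × 4,000 = 320, leaving 92% without a time.

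**3. How closing time shortens delays.** I take time of day to mean the hour of card delivery, the only reading that works for men who never present. Suppose that a man who would come has an exponential delay with mean m, whatever the hour. If W remains before closing, the mean delay among those observed is

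E(D | D ≤ W) = m − W / (exp(W/m) − 1).

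- m = 60 min, W = 360 min: 60 − 360/402.4 = 59.1 min.
- m = 60 min, W = 60 min: 60 − 60/1.718 = 25.1 min.
- m = 15 min, W = 120 min: 15 − 120/2,980 = 14.96 min, so essentially no distortion.

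The direction is always towards shorter delays for late cards. The size depends on W relative to m.

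**4. Range of the artefact.** The documents give no opening hours, card schedule or delay distribution, so these are assumptions: van open 6 hours, cards handed out evenly, exponential delays, no true effect of time of day. The simulation compares cards from the early and late halves of the distribution period among presenters only. The odds ratio (OR) is for a delay over 30 minutes, late versus early.

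| Mean delay (min) | Cards end 2 h before closing: mean early vs late (min), OR | Cards up to closing: mean early vs late (min), OR |
|---|---|---|
| 15 | 15 vs 15, 1.00 | 15 vs 14, 0.79 |
| 30 | 30 vs 29, 0.99 | 30 vs 24, 0.72 |
| 60 | 58 vs 50, 0.92 | 56 vs 37, 0.59 |
| 120 | 93 vs 68, 0.79 | 88 vs 47, 0.46 |
| 240 | 120 vs 80, 0.68 | 111 vs 53, 0.37 |

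Every departure from 1.00 is spurious by construction.

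**The case against.** The strongest reply is that the size is unknown and may be nil. Cards go to men near the van, some within sight of it, so short delays are plausible. If distribution also stops well before closing, the distortion all but disappears. That stands.

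A reader might go further and infer that the time-of-day effect would be mostly an artefact. One could assume a constant hazard that gives 8% presentation over six hours: h = −ln(0.92)/6 = 0.0139 per hour. Mean observed delays are then about 3.0 h for cards given 6 h before closing and 0.5 h for cards given 1 h before, a six-fold contrast. The documents do not support that inference. With cards spread evenly over the six hours, the same hazard implies overall uptake of 1 − 0.08/0.0834, about 4.1%, roughly half the plan's 8%. It also compares two extreme card times.

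Two other readings go too far. One is that the two messages would be compared on delay among presenters; study arm is not among the predictors listed in that sentence. The other is that later-day presentation is excluded by rule. Same-day return is the evident intent, but the date of presentation is also recorded and no exclusion is stated.

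Finally, time to presentation is neither a primary nor a secondary outcome. That limits the weight of the point but does not remove the mismatch between model and outcome.

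**Conclusion.** The concern holds as a defect in a supplementary analysis. Two parts follow directly from the text: logistic regression is named for a duration without a cut-off, and there is no rule for men who do not present, about 89.5% of cards at the planning rates. A third follows from the same-day design: a presenters-only analysis biases the time-of-day effect towards shorter delays for late cards. Its size ranges from negligible (OR 1.00) to large (OR 0.37) under the assumptions above, and the documents do not allow it to be narrowed.

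The primary uptake comparison does not use this outcome and is unaffected. The point should be corrected before analysis, but it does not threaten the trial's main conclusion.

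**What to change.** 1. Remove time to presentation from the logistic regression sentence in the synopsis, and reconcile the synopsis with section 2.5.g so that both name the outcome and its model, or neither does.
2. Record the van's closing time once per clinic day, prospectively. Make sure the recruiter's separate log carries each card's code, so that non-presenters stay in the data.
3. Analyse every card as time-to-event: start at logged delivery, event at presentation, censoring at closing that day. Use Cox or complementary log-log regression with location strata and standard errors clustered by clinic day. State how a presentation on a later date is treated.
4. Use only predictors known for every card: time of day, line of sight, location and recruiter. Age and other questionnaire items exist only for men who present, so they can enter only a descriptive analysis of presenters.
5. State that the hazard ratio combines whether men come with how fast they come. With about 90% of cards censored, it will mostly reflect uptake.

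A simpler alternative keeps logistic regression: pre-specify a binary outcome of presenting within x minutes, among all cards issued at least x minutes before closing, again with clustering by clinic day. It gives up the latest cards and needs x fixed in advance.

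The cost is a revised analysis paragraph, one extra data item per clinic day, a slightly more complex model, and the loss of demographics from the all-card model. Delivery and presentation times are already to be collected.

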## 1. Introduction

South African men have suboptimal levels of HIV testing, antiretroviral therapy (ART) initiation, retention and survival on treatment and have poorer HIV outcomes than their female counterparts, suggesting that these men remain underserved in the context of the HIV response (Cornell, Cox, & Wilkinson, 2015; Cornell et al., 2012; Cornell & Myer, 2013; Johnson et al., 2017). Only 78% of men living with HIV know their status, 67% of those men are on ART and 82% were virally suppressed in 2017 (HSRC, 2018). While the increased focus on key populations, pediatrics, girls and young women has produced a better understanding of their sexual health needs and improved HIV related outcomes (Haal, Smith, & van Doorslaer, 2018), the needs of men in South Africa remain understudied.

ART-based interventions have consistent efficacy and effectiveness data and represent the standard of care for both HIV prevention and treatment in recommendations by UNAIDS, WHO, and the Ministry of Health in South Africa (Bekker et al., 2016; Meintjes et al., 2017). Taking daily ART eliminates enough of the virus so that HIV cannot be detected via viral load testing (Eisinger, Dieffenbach, & Fauci, 2019). Those who have an undetectable viral load cannot transmit the virus to sexual partners or through giving birth (Davies et al., 2018; Eisinger et al., 2019), commonly referred to as U=U (undetectable viral load equals untransmittable virus). Typical communication about and delivery of HIV testing and ART in South Africa has primarily focused on "access" (Sharma, Barnabas, & Celum, 2017) as opposed to promoting uptake and adherence as a rewarding experience. U=U is a message that promotes the reward of knowing one's status (peace of mind) and starting on treatment if diagnosed with HIV to remain healthy and alleviate the stress of HIV transmission to sex partners. The U=U message has been effectively promoted in Europe and North America where people living with HIV describe feeling free of internal and external stigma as a result (The Lancet HIV, 2017). However, awareness of the large prevention effects of ART remains low in many parts of sub-Saharan Africa. Recent studies have shown that many men are unaware that ART can dramatically reduce the likelihood of HIV transmission.

While ART-based interventions are efficacious, the ongoing adverse outcomes among men suggest implementation challenges, including adoption and adherence. Findings from implementation research have recommended differentiated services, focused on dedicated testing and treatment programs tailored to the needs of men, to improve care outcomes (Fakoya, Dybul, & Sands, 2019; Sharma et al., 2017). Yet, there are few rigorous evaluations on the impact of services targeting men, particularly in HIV endemic, low- and middle-income countries.

The behavioral economics (BE) health model (Rice, 2013) suggests that the context in which decisions are made influence those decisions. Health messaging frequently fails to adequately influence behavior because it appeals to dread, which can thwart adaptive health-seeking behavior and lead to vulnerability denial instead (Arndt & Goldenberg, 2017; Millar & Millar, 1995). The BE health model proposes reframing the message to align with desirable outcomes, which eases the decision making context (Rice, 2013). By reframing the message to align with reward-seeking behavior instead of disease detection, the decision and resultant behavior is simplified. Since the U=U message complements this theoretical framework, the overarching goal of the proposed project is to design and adapt a U=U message and to describe its impact on improving HIV testing uptake among men 15 to 39 years old in a high HIV disease burden community in Cape Town, South Africa.

